5.0 Study Procedures

5.1 Study Design

To assess the efficacy of systematic S&R, we propose a two-phase, three-year mixed methods study (Phase One: quantitative, Phase Two: qualitative) to systematically screen Veterans with or at risk for CVD for nine unmet needs, characterize the prevalence of unmet needs and association with outcomes, and compare the effects of two different referral interventions of varying intensity on multiple outcomes.

In **Phase One (Aim 1)** we will survey Veterans about their unmet needs (N=1760) and conduct quantitative analyses of survey, administrative, and clinical data to characterize the prevalence of unmet needs and their association with baseline outcomes (adherence, utilization, and clinical). In **Phase One (Aim 2)**, we will implement a three-armed RCT at three VA sites to compare outcomes among Veterans with one or more unmet needs (N=880) randomized within each site to one of three intervention arms. Trial participants will participate in three surveys, all administered by phone: 1) an initial index unmet need survey; 2) an eight week follow-up survey to assess if participants connected to any new resources since the index screen and if so, to which one(s); and 3) six months after the initial index screen, the unmet need survey will be administered again.

We have the following study arms: 1) Unmet needs screening and provision of a post card with a generic list of VA resources (hereafter: "Screening" arm), 2)

Screening and provision of a post card with a generic list of VA resources plus provision of a tailored Resource Sheet listing available resources to address identified unmet needs (hereafter: “Awareness” arm), or 3) Screening and provision of generic list of VA resources plus provision of a tailored Resource Sheet plus research team SW-supported referral to assist with connection to resources for unmet needs (hereafter: “Assistance” arm). Quantitative analyses will longitudinally compare the effects of the two referral approaches of varying intensity and a generic intervention on the primary outcome of connections to new resources and secondary outcomes of reduction in unmet needs, adherence, utilization, and health outcomes. See **Appendix A** for a more detailed description of the intervention and approach to randomization.

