Step 3 (phone follow-up to recruit, consent, and screen for eligibility): The research team will provide the final list of site-specific eligible Veterans who did not return an opt-out card to the RA situated at each study site. Guided by a phone script (see **Appendix G**), the RA will contact these Veterans by phone up to three weeks following the opt-out card mailing (making up to 5 attempts if they cannot reach the Veteran) to: 1) describe the study, 2) request participation, including potential randomization to one of three study arms if deemed eligible following the initial index screen, participation in subsequent surveys, and possible contact by phone to invite participation in a qualitative interview; and 3) obtain verbal consent. The RA will review the elements of informed consent and answer any questions the potential respondent might have. Among Veterans who verbally consent to participate, the RA will administer the index unmet need screen and, if Veteran is eligible for the RCT (i.e., 1 or more unmet needs) randomize them to one of the three trial arms using the sealed opaque envelope program (see **Appendix A** for details).

Step 4 (recruitment for qualitative interviews; Veterans): Among study participants, we will purposefully sample 60 Veterans to participate in qualitative interviews. Sample selection and recruitment will be conducted on a rolling basis after the 6-month unmet needs re-screen is completed. The study RA will phone selected Veterans, ask for participation in an interview, and among those who accept, schedule an interview time. Note: As part of the RCT informed consent process, participants will be told that they may be contacted by phone to participate in a qualitative interview, which we believe eliminates the need to mail opt-out cards prior to contacting Veterans by phone for this phase of the study. During this initial call we will not re-consent participants but will review and remind potential participants of the purpose of the interviews and the elements of informed consent.

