Statistical Power for Aim 1: With a sample of N=1760 Veterans completing the index unmet needs screening, we will have 80% power to detect small effect sizes ($f^2=.01$; $OR=1.47$) using 2-tailed significance tests at the $\alpha=.001$ level if the intraclass correlation coefficient (ICC) (for the nesting of patients within sites) is negligible, or medium effect sizes ($f^2=.15$; $OR=4.07$) even if the ICC is as high as .02 for testing associations between the presence of each unmet need and sociodemographic, adherence, utilization, and clinical (BP only) variables. HbA1c is anticipated to be a relevant clinical outcome for only 40% of the sample; for HbA1c, we will have 80% power to detect small effect sizes ($f^2=.03$; $OR=1.84$) using 2-tailed significance tests at the $\alpha=.001$ level if the ICC is negligible.

Statistical Power for Aim 2: The power analysis for Aim 2 focused on the primary outcome of connection to resources to address unmet needs. The sample size was determined based on previous research outside VA which found that individuals who completed a screening and referral intervention were 15% more likely (adjusted Odds Ratio (aOR)=2.1) to have enrolled in a new community resource to address unmet needs post-referral compared to patients in the non-intervention arm. In the present study, we will have 80% power to detect an effect of this size (aOR=2.1) across the three arms using 2-tailed significance tests at the $\alpha=.05$ level, even if we assume an attrition rate as high as 50% for the follow-up phone call at 8-weeks post-screen (retained N=440 across all sites and arms) and a conservative ICC value for patients nested within sites of .01. Previous empirical work found ICC values <.0001 when adjusting for a small number of covariates (e.g., race, marital status) to examine new connections to resources to address unmet needs; we intend to collect and use these covariates in the present study as well. Assuming an ICC value of .0001, we will have 80% power to detect an effect as small as an aOR=1.7 if we assume a 50% attrition rate for the 8-week follow-up phone call, or as small as an aOR=2.0 if we assume a 70% attrition rate. We based our attrition rate upon the study team's prior study where Veterans

had low incomes, high unemployment and low educational status, yet only 35% were lost to a follow-up interview.

Quantitative Data Analysis

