All data analysis will be conducted by study team members based in Boston. [name] is the study Data Analyst who will be responsible for developing the analytic data sets and all programming related to descriptive statistics and multivariate models. He will work closely with [name], the statistician who will be responsible for developing the statistical models and overseeing the overall analytic approach. All analysis will be conducted on VINCI.

Aim 1: Describe the prevalence and distribution of nine unmet needs (housing, food insecurity, utility insecurity, transportation, legal needs, employment, safety, social isolation, stress), and identify their associations with baseline sociodemographic characteristics, adherence, utilization and clinical outcomes.

Our primary analysis for Aim 1 will be descriptive. We will use data obtained during the index screening (N=1760) to generate descriptive statistics (e.g., proportions, 95% confidence intervals (CIs) to characterize the prevalence and distribution of each of the nine unmet needs at baseline across all study sites. We will next conduct inferential analyses to examine associations between unmet needs and sociodemographic characteristics as well as baseline outcomes (i.e., adherence, utilization, and clinical outcomes drawn from CDW data in the 12-months before the index screening for each Veteran). Hierarchical Linear Modeling will be used to control for the nesting of patients within sites, and patient-level variables will be treated as random effects. Hierarchical Generalized Linear Modeling (HGLM) will be used as appropriate to handle binary variables. Variables found to have statistically significant associations with unmet needs will be entered into multivariable models to better understand the correlates of each need. Bonferroni-corrected significance levels will control for multiple comparisons.

Aim 2: Compare the effectiveness of varying intensity referral strategies to address unmet needs on the primary outcome of connection to new resources to address unmet needs, and on secondary outcomes of post-intervention change in unmet needs, adherence, utilization, and clinical outcomes

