Our primary Aim 2 analysis will compare *connection to new resources* at 8-weeks post-index screen (our primary outcome of interest) across the study arms. HGLM will be used to control for the nesting of patients within sites. In all models, patient-level intercepts and slopes will be treated as random effects. We predict significantly greater connection to new resources in the ASSISTANCE arm

compared to the SCREENING arm, with the AWARENESS arm falling intermediate to these other two study arms.

Adherence, Utilization, and Clinical Outcomes. We will also conduct a series of secondary analyses to examine whether the study arms influence more distal outcomes, including adherence, utilization, and clinical outcomes. Specifically, to assess the impact of our intervention on more distal healthcare outcomes, we will use a difference-in-difference approach to examine whether changes from baseline at 6-months and 12-months post-referral differ across the three arms of our RCT (N=880). A series of HLM/HGLM analyses with patients nested within sites will examine differences in change from baseline across arms for the adherence, utilization, and clinical outcomes. As with the other analyses, all models will treat patient-level intercepts and predictors as random effects. We will have 80% power to detect small-to-medium effects ($f^2=.05$; OR=2.28) across the three arms using 2-tailed significance tests at the $\alpha=.05$ level, even if we assume a conservative ICC value for patients nested within sites of .01. HbA1c is anticipated to be a relevant clinical outcome for only 40% of the sample and we anticipate missing HbA1c test data for 17% of these Veterans in the year following their index screen; thus, for HbA1c, we will have 80% power to detect small-to-medium effects ($f^2=.08$; OR=2.71) across the three arms using 2-tailed significance tests at the $\alpha=.05$ level, even if we assume a conservative ICC value for patients nested within sites of .01.

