Examining marginal intervention effects over and above S&R occurring as part of usual care. Finally, given that Veterans may already be accessing resources for some unmet needs as part of usual care and related to existing screening for homelessness and food insecurity, we will conduct supplemental analyses to examine whether our intervention effects hold when controlling for use of VA SW services not attributable to the present intervention (e.g., services already being accessed separate from the study intervention). Although we will specifically be assessing connection to new resources following the S&R mechanisms in our three study arms, it is possible that individuals already connected to certain resources will be more likely to seek out additional support/resources (e.g., because they already have successful experiences using VA resources to meet certain unmet needs) or less likely to seek out additional support/resources (e.g., because they feel they already have the support they most need). Because VA screens for housing and food insecurity, Veterans may already be accessing resources for these. To examine whether the intervention has a significant impact on connection to new resources, unmet need reduction, and more distal health outcomes when controlling for use of VA SW services not attributable to the present study, we will conduct supplemental analyses that control for connection to resources associated with each of our nine unmet needs prior to enrollment in our intervention. Use of SW resources not attributable to our study will be measured via CPRS encounter forms, where SWs record encounters with patients, and from referral/consult documentation available in CPRS during the 12 months prior to the start of our intervention.

Qualitative Data Analysis

Aim 3: Identify barriers and facilitators to Veterans' connecting with resources to address unmet needs and getting needs met, and explore potential explanatory factors related to the relative success of each study arm.

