Appendix A: Description of the Intervention and Randomization

Unmet Needs Screen:

Veterans (anticipated N=1760) will be screened for unmet needs (index screen) and those identified as having at least one unmet need (target N=880) will be randomized to one of three study arms and screened again 6-months later. We will use the sealed opaque envelope program to generate randomization. For the index screen, a study Research Assistant (RA) will administer the screening instrument to Veterans by phone prior to the Veteran's upcoming primary care (PC) clinic appointment to gather data on nine unmet needs (full screen in **Appendix I**). Six months after the index screen, the RA will re-screen each Veteran participant by phone. For each completed screen, we will provide Veterans \$15 for their time.

After the RA determines each participant is eligible (see Section 5.2. Recruitment Methods), randomization will occur by the RA opening sealed envelopes that reveal the treatment assignments (screening, awareness, or assistance). Envelopes will be opened for each participant in the order they are recruited. The RA will then inform the participant of their assignment.

Resource Sheets:

For Veterans in the Awareness and Assistance arms, the RA will provide (via U.S mail) Resource Sheets tailored to the unmet needs identified in the index screen. During the index screen (by phone), the RA will inform the Veteran that they will receive a Resource Sheet in the mail and mail the Resource Sheets to the Veteran within two days of the index screen. During the index screen, the RA will additionally ask the Veteran if they would also like to receive the Resource Sheets via email. For Veterans who respond affirmatively, the RA will send the Resource Sheets as an email attachment during the index screen phone call and offer to review its content with them. The email message will be sent via encrypted email and will not solicit reply. (**Appendix G** contains the phone script for this interaction, and **Appendix P** contains the Resource Sheet email text and the cover letter for mailing.)

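### Secondary outcomes analysed as continuous values are compared as change from baseline; adjusting for the baseline value is equally or more precise and needs no new data

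*Combined protocol and SAP*

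**What the plan says.** Under Adherence, Utilization, and Clinical Outcomes, section 5.6 plans that "we will use a difference-in-difference approach to examine whether changes from baseline at 6-months and 12-months post-referral differ across the three arms". The model follows in the next sentence: "A series of HLM/HGLM analyses with patients nested within sites will examine differences in change from baseline across arms".

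The baseline values will be in hand. The Aim 1 text of the same section describes baseline adherence, utilization and "clinical outcomes drawn from CDW data in the 12-months before the index screening for each Veteran".

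The covariates named elsewhere are different variables. The Aim 2 power paragraph cites earlier work "adjusting for a small number of covariates (e.g., race, marital status) to examine new connections to resources to address unmet needs" and intends to use the same covariates, but this concerns the primary outcome. The usual-care paragraph adds "supplemental analyses that control for connection to resources associated with each of our nine unmet needs prior to enrollment in our intervention", again not the outcome's own baseline.

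Allocation is by individual. Section 5.1 has Veterans "randomized within each site to one of three intervention arms"; in section 5.2 the research associate is to "randomize them to one of the three trial arms using the sealed opaque envelope program"; Appendix A adds "Envelopes will be opened for each participant in the order they are recruited". A parenthesis in section 3.0 puts randomization at site level, but the procedures describe one envelope per Veteran, and that is the reading used here.

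**The concern.** A difference-in-difference comparison is built for groups that may start from different levels. Randomization makes the expected baseline difference zero, so that protection is not needed here. It has a price: subtracting the whole baseline fixes the slope of follow-up on baseline at 1. When the true slope is below 1, as with any regression to the mean, the change score carries baseline noise that an estimated slope would remove.

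What is at stake is precision. The distal part of hypothesis H1 rests on these outcomes, and the mediation analyses in section 5.6 are run only if arm differences in distal outcomes appear. HbA1c has the smallest sample among them, so avoidable variance costs most there.

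**Working it through.** **Inputs from section 5.6.** 880 Veterans randomized, 293 per arm; two-sided alpha .05; 80% power; ICC .01; three sites; detectable f² .05 (OR 2.28) for the distal outcomes and .08 (OR 2.71) for HbA1c; HbA1c relevant for 40%, with 17% of those missing a test in the following year. The documents give no SD and no baseline to follow-up correlation, so both are assumed over a range.

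**The plan's own figures.** Take effective N = N / [1 + (N/3 − 1) × ICC], noncentrality f² × effective N, and OR = exp(2f × π/√3).

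- Distal outcomes: design effect 1 + (293.3 − 1) × .01 = 3.92; effective N = 880 / 3.92 = 224. With 3 numerator df the detectable f² is .0495 (OR 2.24), and power at f² = .05 is 80.5%.
- HbA1c: 880 × .40 × .83 = 292; design effect 1.96; effective N = 149; detectable f² .0753 (OR 2.71).

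The stated figures reproduce apart from rounding and a small gap in the distal OR (2.24 against 2.28). With 2 numerator df, the usual count for three arms, power at f² = .05 is 85.5%, so the plan's figure is slightly conservative.

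**Variance of the two contrasts.** Let s² be the follow-up variance, k = baseline SD / follow-up SD, and ρ the correlation.

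- Change score: (1 + k² − 2ρk) s²
- Baseline-adjusted: (1 − ρ²) s²
- Ratio, adjusted / change: (1 − ρ²) / (1 + k² − 2ρk)

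The denominator equals (1 − ρ²) + (k − ρ)², so the ratio cannot exceed 1. It equals 1 only when k = ρ, which is a slope of ρ/k = 1. Example at ρ = .7, k = 1: .51 / .60 = .85.

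| k | ρ = .3 | ρ = .5 | ρ = .7 | ρ = .9 |
|---|---|---|---|---|
| 0.8 | .784 | .893 | .981 | .950 |
| 1.0 | .650 | .750 | .850 | .950 |
| 1.2 | .529 | .605 | .671 | .679 |

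A simulation (N = 292, three arms, site fixed, 4,000 runs) gave .64, .85 and .96 at k = 1 for ρ = .3, .7 and .9, and 1.00 at k = ρ = .7 and at k = ρ = .9. Mean bias was below .01 SD for both estimators.

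**What this means for HbA1c.** At most 292 Veterans, about 97.4 per arm, have any value in the following year. The detectable pairwise difference is 2.80 × √(2 × variance / n), in follow-up SD units, with no design effect. At ρ = .7, k = 1: 2.80 × √(2 × .60 / 97.4) = .311 for change and 2.80 × √(2 × .51 / 97.4) = .287 adjusted.

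| k = 1 | ρ = .3 | ρ = .5 | ρ = .7 | ρ = .9 |
|---|---|---|---|---|
| Change, 97.4 per arm | .475 | .401 | .311 | .180 |
| Adjusted, 97.4 per arm | .383 | .348 | .287 | .175 |
| Change, 48.7 per arm | .672 | .568 | .440 | .254 |
| Adjusted, 48.7 per arm | .542 | .492 | .405 | .247 |

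The lower pair assumes that only half have a value at a given time point; the plan does not give that number. The variance ratio itself does not depend on n.

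**On the plan's power scale.** If f² = .05 refers to the change score, with k = 1, 3 df and effective N 224, power rises from 80% to about 95%, 91%, 87% and 83% at ρ = .3, .5, .7 and .9.

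**Whether the multilevel model already recovers the loss.** For three time points with exchangeable correlation, an arm-by-time model with a free baseline mean in each arm has exactly the change-score variance. Constraining the baseline means to be equal gives exactly the adjusted variance (ratios .65, .75, .85 and .95). Random intercepts alone do not close the gap.

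**The case against.** The strongest reply is that nothing here is an error. The change contrast is valid, the outcomes are secondary, and the trial is sized on connection to resources. No stated power target is shown to be missed: without the design effect, power at f² = .08 with 292 Veterans is about 99%. All of this stands, and it limits the point to an improvement.

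Second, the point applies only to continuous outcomes, and the plan does not say which these are. It quotes both f² and OR, allows hierarchical generalized models, and section 2.0 speaks of glycemic control, which could be a binary state. If BP, HbA1c and adherence are all dichotomized, the variance result does not carry over. That stands too, and is itself a reason to state the outcome types.

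Third, the wording does not exclude adjustment. Change regressed on arm and baseline gives the same arm estimate as follow-up regressed on arm and baseline, the predictors are not listed in full, and the Data Analysis Plan mentioned in section 5.1 is not visible. This is possible, but the ordinary reading of difference-in-difference is an unadjusted change contrast, and nothing visible says otherwise.

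Finally, the gain may be small: 2% at ρ = .7, k = .8, and nil at k = ρ. True, but in large samples it is never a loss.

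**Conclusion.** The concern holds as an efficiency improvement that should be made. For any of BP, HbA1c or adherence analysed as a continuous value, the planned contrast is unbiased but no more precise than a baseline-adjusted one, and less precise unless the slope is 1. The variance saving runs from nil to about 47% over assumed ρ of .3 to .9 and k of .8 to 1.2; with equal SDs it is 5% to 35%. The conclusion rests on individual randomization within site, large-sample precision, and the reading that section 5.6 describes an unadjusted change contrast. Where the saving falls in that range cannot be settled from the documents. Nothing is claimed about binary or count outcomes.

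**What to change.** In section 5.6, state for BP, HbA1c and adherence whether each is analysed as continuous. For those that are, model the 6- and 12-month values on arm, site and the Veteran's own baseline value. Alternatively, use a longitudinal model with baseline means constrained equal across arms, which also keeps Veterans who have no baseline value. State the rule for missing CDW baselines and report the change-score result as a sensitivity analysis. If the Data Analysis Plan already adjusts for baseline, align section 5.6 with it. Settle the wording before outcome data are examined, so that the choice of estimator is not made after the fact.

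The cost is plan wording, one degree of freedom per model and a missing-baseline rule; no new data are needed. Missing baselines do not favour the current plan, since a Veteran without a baseline has no change score either.

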VAs' lack of systematic and comprehensive S&R for unmet needs also means missed opportunities to better understand the scope and scale of unmet needs across the entire VA patient population, as no such data exists.¹⁴ This in turn limits VA's understanding of how best to support and target SW services. It is also unknown whether a lower-intensity referral process (i.e., provision of tailored paper Resource Sheets to address unmet needs instead of a referral to SW) can help some Veterans to the same extent it helps patients in non-VA care settings.

^{10, 16} Thus, a critically important dimension of the study we propose is to test whether for some Veterans, a less intense intervention is adequate. If so, this has valuable implications for resource allocation decisions and future implementation.

To address these knowledge gaps, we propose a **randomized controlled trial (RCT)** to systematically screen Veterans with/at risk for CVD for nine unmet needs, characterize the prevalence of unmet needs and associations with outcomes, and compare the effect of two different intensity referral interventions. Our primary outcome is Veterans' connections to new resources to address unmet needs. Additional outcomes include unmet need reduction, adherence (medications, ambulatory care appointments), utilization (preventable hospitalizations, urgent care), and clinical outcomes (blood pressure, glycemic control).

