Unmet Need Reduction: Similar analyses will be used to examine differences across our three study arms in change from baseline in the proportion of unmet needs among the sub-sample of participants who complete the re-screening at 6-months post-referral. Among this sub-sample (N=220, assuming attrition rates of 50% at both the 8-week and 6-month follow-up phone surveys), we will have 80% power to detect a small-to-medium effect ($f^2=.09$; OR=2.94) across the three arms in terms of unmet need reduction using 2-tailed significance tests at the $\alpha=.05$ level, even if we assume a conservative ICC value for patients nested within sites of .01.

Differences in Intervention Effectiveness. In addition to examining how the S&R influences connection to new resources, we will conduct additional analyses to examine whether there is differential impact between the two referral arms (Awareness and Assistance) on connection to new unmet needs resources; unmet need reduction; and adherence, utilization and clinical outcomes among Veterans with certain unmet needs or with fewer unmet needs. While we predict that providing SW support (Assistance arm) will generally have a larger impact on outcomes than providing a Resource Sheet alone (Awareness arm), it would be beneficial to know if the Resource Sheet alone (or even the screening and

provision of generic list of resources) is sufficient to produce comparable changes in outcomes among Veterans with certain unmet needs or among Veterans with fewer unmet needs. If true, future implementation research could create tailored interventions that funnel the resources for more time- and cost-intensive referral strategies to only those Veterans who need it most.

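### The analysis by type and number of needs compares Awareness with Assistance only, so it cannot by itself show that the Resource Sheet is sufficient in a group of Veterans

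*Combined protocol and SAP*

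**What the plan says.** Section 2.0 gives this question weight: "a critically important dimension of the study we propose is to test whether for some Veterans, a less intense intervention is adequate".

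Section 5.6, under Differences in Intervention Effectiveness, defines the analysis meant to answer it. It will examine "whether there is differential impact between the two referral arms (Awareness and Assistance) on connection to new unmet needs resources", and also on unmet need reduction and on "adherence, utilization and clinical outcomes among Veterans with certain unmet needs or with fewer unmet needs". The sentence after that states the purpose more widely. Besides the sheet on its own, it asks about the lowest-intensity arm, in these words: "provision of generic list of resources) is sufficient to produce comparable changes in outcomes among Veterans with certain unmet needs". If so, later implementation work could "funnel the resources for more time- and cost-intensive referral strategies to only those Veterans who need it most".

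The Screening arm does appear in the whole-sample analyses. Section 5.1 will "compare the effects of the two referral approaches of varying intensity and a generic intervention on the primary outcome", and the primary analysis in section 5.6 compares connection ("our primary outcome of interest) across the study arms"). Distal outcomes and unmet need reduction are also compared across three arms, the latter among those re-screened. None of these is specified by type or number of needs. The plan gives no sample size, power, margin or criterion for calling one strategy sufficient or comparable in a group.

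**The concern.** Two adjacent sentences do not match. The question covers three levels of intensity, while the specified contrast covers the upper two.

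For the Resource Sheet, sufficiency has two parts: the sheet achieves something over the Screening arm, and adding a social worker achieves little more. Awareness v Assistance addresses only the second part. A group in which the sheet and the social worker help equally and a group in which neither helps give the same expected difference, zero. More data or a well-chosen margin would not separate them, because the missing information is in the arm left out of the contrast.

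At stake is the reading of a question that the protocol ranks highly and links to the targeting of social work support. Followed literally, the analysis could lead a report to call the sheet enough in a group where it was never shown to do anything.

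**Working it through.** **1. Which effects the contrast identifies.** Write Sc, Aw and As for the true outcome in the Screening, Awareness and Assistance arms within a group. The specified contrast is As − Aw. If differential impact is read instead as a comparison of each arm's effect relative to Screening, the result is (As − Sc) − (Aw − Sc) = As − Aw. Screening cancels, so that reading adds nothing.

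**2. Inputs.** From section 5.6: 880 randomised (293 per arm), 440 retained at 8 weeks (440/3 = 146.7 per arm), aOR 2.1, 80% power, two-sided 0.05. The control rate is not given. I read the cited 15% as 15 percentage points and solve with OR 2.1:

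2.1p/(1 + 1.1p) − p = 0.15, so 1.1p² − 0.935p + 0.15 = 0, and p = 0.215 or 0.635.

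The first root gives 21.5% v 36.5%. The second gives 63.5% v 78.5%, the mirror image, with the same power. Both rest on that reading, so a range of control rates is shown below.

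**3. Anchor.** The plan has no power figure for the by-need analysis, so I check its primary-outcome figure. Power = Φ[(d − 1.96·se0)/se1], with d = 0.15 and pooled rate 0.29:

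- se0 = √(0.29 × 0.71 × 2/146.7) = 0.0530
- se1 = √((0.215 × 0.785 + 0.365 × 0.635)/146.7) = 0.0523
- Power = Φ[(0.15 − 0.1038)/0.0523] = Φ(0.88) = 81%

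This agrees with the stated 80% for one pair of arms, at this assumed rate and with no inflation for site clustering.

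**4. What each contrast would show.** Chance of a significant result at 147 per arm:

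| True pattern (Sc / Aw / As, %) | Aw v As | Aw v Sc | As v Sc |
|---|---|---|---|
| Neither referral arm helps (21.5 / 21.5 / 21.5) | 5% | 5% | 5% |
| Sheet is enough (21.5 / 36.5 / 36.5) | 5% | 81% | 81% |
| High in every arm (36.5 / 36.5 / 36.5) | 5% | 5% | 5% |
| Only the social worker helps (21.5 / 21.5 / 36.5) | 81% | 5% | 81% |

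The specified contrast behaves identically in the first three rows, at any group size. The contrasts with Screening separate row 2 from row 1. No contrast separates row 3 from row 1. Only the absolute rates differ there, and every arm receives screening and the postcard (section 5.1; section 5.2 mails the postcard before the recruitment call).

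**5. Precision within groups.** Group sizes are assumptions. Power is for Awareness v Screening at OR 2.1, by the formula in step 3. The interval is exp(ln 2.1 ± h), with h = 1.96·√(1/(n·p0·q0) + 1/(n·p1·q1)), where q = 1 − p. At 73 per arm, h = 1.96·√(0.0808 + 0.0589) = 0.73, against ln 2.1 = 0.74.

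| Share of the 440 | Per arm | Power at 21.5% | Power, control rate 10% to 50% | 95% CI if the estimate is OR 2.1 (at 21.5%) |
|---|---|---|---|---|
| All | 147 | 81% | 59% to 89% | 1.25 to 3.53 |
| 50% | 73 | 52% | 33% to 61% | 1.01 to 4.37 |
| 30% | 44 | 34% | 22% to 40% | 0.82 to 5.41 |
| 20% | 29 | 24% | 16% to 29% | 0.66 to 6.69 |

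Power is lowest at a 10% control rate and highest near 40%.

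For Assistance v Awareness with both at 21.5%, the 95% interval for the difference has half-width 1.96·√(2 × 0.215 × 0.785/n), which is 13 points at 73 per arm and 21 points at 29.

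**The case against.** The case for the plan has force on several points.

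- A reader might infer that the plan drops the Screening arm. It does not. The statement of purpose names the generic list, no model is said to exclude that arm, and the whole-sample analyses use all three. What is missing is narrower: a within-group contrast with Screening.
- A reader might infer that Veterans helped by neither strategy would be classified as adequately served and denied social work. The documents contain no classification rule. These are additional analyses meant to inform later research. Where neither arm beats Screening, not directing social work there would even fit the trial's evidence. The error would lie in describing the sheet as enough.
- A reader might infer that the two situations would look identical in a report. Only the specified difference is the same. Arm-level connection would differ (21.5% v 36.5% under the assumption here). Those levels do not give an effect of referral without Screening as comparator, but they would be visible.
- A reader might infer that adding Screening settles whether the generic list suffices. It cannot, because no arm goes without screening and the postcard.
- Power within groups is low, and extra contrasts add multiplicity. Both are true. They argue for estimation labelled exploratory, not for omitting a randomised third of the data from the comparison.

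What remains is that the plan states a three-level question and specifies a two-level contrast.

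**Conclusion.** The concern holds in this limited form. As specified, a zero Awareness v Assistance difference in a group is equally consistent with both strategies helping and with neither improving on Screening. It cannot alone support a claim that the Resource Sheet is sufficient there. That follows from the form of the contrast and needs no assumed rate.

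The numerical illustration does rest on assumptions: a control rate of 21.5% inferred from aOR 2.1 and a 15-point difference, chosen group shares, independent responders, and connection at 8 weeks as the outcome. Under these, Awareness v Screening distinguishes the two situations well only in the full responder sample and weakly in small groups. Precision differs for other outcomes. The distal outcomes are planned on all 880, whereas need reduction has about 73 per arm in total (220/3).

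The point warrants an amendment to a secondary analysis. It does not affect the primary comparison.

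**What to change.** Amend Differences in Intervention Effectiveness in section 5.6 as follows:

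- Fit the moderator models with all three arms: three-level arm by need type, and three-level arm by number of needs.
- For each group report Awareness v Screening, Assistance v Screening and Assistance v Awareness, together with the absolute arm-level rates, all with confidence intervals and labelled exploratory.
- Describe the Resource Sheet as sufficient only where Awareness improves on Screening and the interval for Assistance v Awareness is compatible with comparability. Because the plan gives no margin, state beforehand what counts as comparable. Requiring only that Awareness or Assistance beats Screening would not do, since it is met when the social worker alone works.
- Where neither referral arm differs from Screening, report no demonstrated added benefit of referral. Do not report that the generic list suffices.

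Cost: no new data or participants. There are more contrasts to report, for example 27 rather than 9 per outcome across nine need types (3 × 9), plus those for number of needs. The Bonferroni statement in section 5.6 is under Aim 1 and no correction is stated for Aim 2, so the exploratory label matters. Intervals will be wide, and in small groups the usual honest answer will be that sufficiency is undetermined.
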